3.7.1.2 Quality of life analyses

Analysis for Quality of Life endpoints are included in [Section 3.4](#).

3.7.1.3 Biomarker analyses

The biomarker analyses will be performed using PDy population defined in [Section 2](#).

The following biomarkers will be evaluated if applicable:

- Peripheral blood soluble biomarkers (including but not limited to hsCRP, IL-17A, IL-17F, IL-22, IL-19) from baseline to Week 4 and 12

• [REDACTED]
[REDACTED]

The following analyses will be performed if applicable:

- Descriptive statistics by treatment arm at baseline, intermediate timepoints and end of treatment
- Plots of fold changes from baseline in soluble protein biomarkers per treatment arm and visit
- Appropriate statistical methods based on the sample size such as linear mixed models, ANOVA (parametric), Kruskal-Wallis test, Wilcoxon signed rank test (non-parametric)
- Correlation of (a) biomarker results at baseline and (b) changes of biomarker results from baseline to post treatment visits with participant's clinical parameters

If measurement values below LLoQ occur, then the number of these values will be reported, computations and plots will be conducted setting values below LLoQ to LLoQ/2 and corresponding points in plots will be marked by dedicated symbols.

Additional analysis for the biomarkers listed above and other exploratory biomarkers (eg, gene expression and proteomics data and DNA genotype data) may be performed and will be summarized in a separate document.

3.7.2 Subgroup analyses

Subgroup analyses of the primary efficacy endpoint will be performed to assess the homogeneity of the treatment effect across the following subgroups (categories with fewer than 30 participants may be combined with other categories):

- Region (Western Countries, Latin America, Rest of world)
- Hispanic ethnicity (Hispanic or Latino, Not Hispanic or Latino)
- Age group (≥ 18 to <40 , ≥ 40 to <60 , ≥ 60 to ≤ 75 , >75 years)
- Gender (Male, Female)
- Baseline body mass index (BMI) level (<30 , ≥ 30 kg/m²)
- Baseline PASI score (≤ 15 , >15)
- Baseline PASI score (≤ 20 , >20)

Treatment-by-subgroup interaction term and the subgroup factor term will be added in the primary model. In the case that the subgroup factor is identical or similar to a randomization strata factor, the strata factor will not be kept in the model.

The treatment effects (SAR441566 versus placebo) for the primary endpoint will be provided, as well as the corresponding 95% CI, for each subgroup, using the same method as applied to the primary analysis. Forest plots may be provided.

3.8 INTERIM ANALYSES

No interim analysis will be performed.

3.9 CHANGES TO PROTOCOL-PLANNED ANALYSES

1. The exploratory/tertiary endpoint “PASI change from baseline to Week 4 and 8” in Table 1 from the protocol dated 25-Apr-2024 has been updated to “PASI percent change from baseline to Week 4 and 8” in this SAP, to be aligned with the secondary endpoint.
2. Due to the fast enrollment, the final analysis will be performed 5 months ahead of original timeline at the time the interim analysis was planned. Hence, the interim analysis planned in the protocol dated 25-Apr-2024 is considered unnecessary by the project team and Therapeutic Area Immunology&Inflammation leadership and is cancelled.

4 SAMPLE SIZE DETERMINATION

A total sample size of approximately 207 participants will be randomized to the intervention groups in two different strata, ie, NTIP vs. ETIP.

In the stratum of NTIP, approximately 144 participants will be randomized in a randomization ratio 1:1:1:1:1:1 to SAR441566 200 mg BID, SAR441566 100 mg BID, SAR441566 200 mg QD, SAR441566 100 mg QD, SAR441566 50 mg QD and placebo, ie, 24 participants in each of six groups. The NTIP is the primary population for efficacy analysis.

In the stratum of ETIP, approximately 63 participants will be randomized in a randomization ratio 2:2:2:1 to SAR441566 200 mg BID, SAR441566 200 mg QD, SAR441566 100 mg QD and placebo, ie, 18 participants in each of SAR441566 200 mg BID, 200 mg QD and 100 mg QD groups and 9 participants in the placebo group. The ETIP is for exploratory purpose only.

In the NTIP, assuming a 10% dropout rate, the sample size of 24 participants per group will provide about █% power to demonstrate superiority of SAR441566 200 mg BID or 100 mg BID or 200 mg QD versus placebo with a 2-sided significance level of 0.05, based on Chi-square test with the following assumptions on the primary endpoint:

- PASI75 Placebo rate of █%.
- PASI75 SAR441566 rate of █%.

To estimate the dose-response curve on QD regimen in the NTIP, the sample size of 24 participants per group will provide an minimum power of █% to detect the presence of a dose response, based on the assumption of a maximum effect in terms of PASI75 of treatment difference of █% in SAR441566 comparing with placebo rate of █%, using █
█
█.

Calculations for Chi-square test were done using █
█

5 SUPPORTING DOCUMENTATION

5.1 APPENDIX 1 LIST OF ABBREVIATIONS

AE:	adverse event
AESIs:	adverse events of special interest
ALT:	alanine aminotransferase
ANCOVA:	analysis of covariance
AST:	aspartate aminotransferase
BID:	bis in die - twice a day
BMI:	body mass index
BSA:	body surface area
CI:	confidence interval
CMH:	Cochran-Mantel-Haenszel
DLQI:	dermatology life quality index
DNA:	deoxyribonucleic acid
ECG:	electrocardiogram
ETIP:	Experienced targeted immunotherapy population
HLGT:	high-level group term
HLT:	high level term
hsCRP:	high-sensitivity C-reactive protein
ICE:	Intercurrent event(s)
ICF:	informed consent form
IL:	interleukin
IMP:	investigational medicinal product
ITT:	intent-to-treat
IWRS:	interactive web response system
LLOQ:	lower limit of quantitation/detection limit
LLT:	lower-level term
MCP-Mod:	Multiple Comparisons Procedure - Modelling
MedDRA:	medical dictionary for regulatory activities
MTX:	methotrexate
NTIP:	Naive targeted immunotherapy Population
PCSA:	potentially clinically significant abnormality
PK:	pharmacokinetic
PPASI:	palmoplantar psoriasis area and severity index
PT:	preferred term
QD:	quaque die - once a day
RNA:	ribonucleic acid
SAE:	serious adverse event
SAP:	statistical analysis plan
SD:	standard deviation

SOC:	system organ class
SPGA:	static Psoriasis Global Assessment
TE:	treatment-emergent
TEAE:	treatment-emergent adverse event
TNFR:	tumor necrosis factor receptor
ULN:	upper limit of normal
ULOQ:	upper limit of quantification
WHO-DD:	World Health Organization-drug dictionary
WOCF:	worst observation carried forward

5.2 APPENDIX 2 PARTICIPANT DISPOSITIONS

The number (%) of participants included in each of the analysis populations listed in [Table 3](#) will be summarized.

Screen failures are defined as participants who consent to participate in the study but are not subsequently randomized. The number (%) of screen failures and reasons for screen failures will be provided in the screened population.

The number (%) of participants in the following categories will be provided:

- Exposed and not randomized participants
- Randomized participants
- Randomized but not exposed participants
- Randomized and exposed participants
- Participants who completed the 12-week study treatment period as per protocol
- Participants who did not complete the 12-week study treatment period as per protocol, main reason for permanent intervention discontinuation and main reason for treatment withdrawal by subject
- Participants who completed the study period as per protocol.
- Participants who did not complete the study period as per protocol and main reason for study discontinuation.

Reasons for permanent study intervention and study discontinuation “adverse event” and “other reasons” will be split as related versus not related to COVID-19, if applicable.

In addition, the number (%) of participants screened, screened-failed, randomized, with permanent IMP discontinuation and with early study discontinuation will be provided by country and by country/site.

Protocol deviations

Critical and major protocol deviations (automatic or manual) will be summarized in the randomized population.

5.3 APPENDIX 3 DEMOGRAPHICS AND BASELINE CHARACTERISTICS, PRIOR OR CONCOMITANT MEDICATIONS

Demographics, baseline characteristics, medical surgical history

The following demographics and baseline characteristics, medical and surgical history and disease characteristics at baseline will be summarized using descriptive statistics in NTIP/ETIP population and overall.

Demographic and baseline characteristics

- Age in years as quantitative variable and in categories (From 18 - 39 years, From 40 - 59 years, From 60 - 75 years, 76 years and over)
- Sex (Male, Female)
- Race (White, Black or African American, Asian, Native Hawaiian or other Pacific Islander, American Indian or Alaska native, Not reported, Unknown)
 - Asian subcategories (Chinese, Japanese, Asian Indian, Korean, Other Asian Origin)
 - Other Asian Origin subcategories (Asian Origin Not reported, Asian Origin Unknown)
- Ethnicity (Hispanic or Latino, Not Hispanic or Latino, Not Reported, Unknown)
- Region (Western country, Latin America, Rest of World)
 - Western country includes Bulgaria, Canada, Czech Republic, Georgia, Germany, Hungary, Poland, Portugal, Spain, Turkey, United Kingdom and USA
 - Latin America includes Argentina and Chile
 - Rest of world includes China, Japan and Mauritius
- Body weight as quantitative variable (kg) and in categories (<70, ≥70 to <90, ≥90 kg)
- Body mass index as quantitative variable (kg/m²) and in categories (<18.5, ≥18.5 to <25, 25 to <30, ≥30 kg/m²)
- Smoking habit (Never, Former, Current)
- Alcohol Habit: Alcohol drinking frequency (Never, Occasional, At least monthly, At least weekly and At least daily) and number of standard alcohol drinks on a typical day when drinking (1 or 2, >2)
- HIV and Hepatitis screen: HIV-1 and HIV-2 antibodies, hepatitis B surface antigen, hepatitis B core antibody, hepatitis-C antibodies

Baseline safety and efficacy parameters (apart from those listed above) will be presented along with the safety and efficacy summaries.

Medical (or surgical) history includes all the relevant medical (or surgical) history during the lifetime of the participant. Medical and surgical history will be coded to a LLT, PT, HLT, HLGT, and associated primary SOC using the MedDRA version in effect at Sanofi at the time of database lock.

Disease characteristics at baseline

- Age at diagnosis of psoriasis (years) as quantitative variables defined as:
(date of diagnosis* – date of birth+1)/365.25.
- Age at diagnosis of psoriasis (years) in categories (Before 18 years, From 18 – 39 years, From 40 – 59 years, From 60 – 75 years, 76 years and over)
- Time since diagnosis of psoriasis (years), defined as:
(date of ICF – date of diagnosis*+1)/365.25.
- PASI score
- sPGA score
- BSA score
- Prior systemic treatment use (Yes or No)
 - If yes, description of the three following categories:
 - TNFi biologics
 - Other biologics [IL-12, IL-17, IL-23 biologics]
 - Small molecules [phosphodiesterase 4, janus kinase, tyrosine kinase 2 inhibitors]

*In case the day of diagnosis would be missing, it will be imputed as to 01. In case the month and day of diagnosis would be missing, it will be imputed as 01JANUARY if the year of diagnosis equals the year of informed consent; it will be imputed as 01JULY if the year of diagnosis does not equal the year of informed consent.

Prior or concomitant medications

All medications will be coded using the World Health Organization-Drug Dictionary (WHO-DD) using the version currently in effect at Sanofi at the time of database lock.

- Prior medications are those the participant received prior to first IMP intake. Prior medications can be discontinued before first administration or can be ongoing during treatment period.
- Concomitant medications are any medications received by the participant concomitantly to the IMP from the first administration of IMP to the last IMP intake + 1 day.
- Post-treatment medications are those the participant received in the period running from the end of the concomitant medications period up to the end of the study.
- A given medication can be classified as a prior medication and/or as a concomitant medication and/or as post-treatment medication. If it cannot be determined whether a given medication was taken prior or concomitantly or post, it will be considered as prior, concomitant, and post-treatment medication.

The prior and concomitant and post-treatment medications will be summarized for the randomized and exposed population, by anatomic and therapeutic level. Participants will be counted once in each ATC category (anatomic or therapeutic) linked to the medication.

5.4 APPENDIX 4 DATA HANDLING CONVENTIONS

Analysis windows for time points

The following analysis windows will decide how the scheduled and/or unscheduled visits will be used in the by-visit analyses of efficacy and safety.

A measurement (scheduled or unscheduled) will be used if it is available and measurement date is within the analysis window, except for vital signs, laboratory test and ECG for which only scheduled measurement will be used.

After applying these time windows, if multiple assessments are associated to the same time point, the closest from the targeted study day will be used. If the difference is a tie, the value after the targeted study day will be used. If multiple valid values exist within a same day, then the first value of the day will be selected.

If there is no measurement for a given parameter in an analysis window, data will be considered missing for the corresponding visit.

Table 8 - Time-window definition for safety endpoints analyses

Scheduled visit	Analysis visit	Targeted study day	Time-window (days)
			Vital signs, laboratory tests, 12-lead ECG and Targeted Physical examination
Week 2 (Visit 3)	Week 2	15	2-21
Week 4 (Visit 4)	Week 4	29	22-42
Week 8 (Visit 5)	Week 8	57	43-70
Week 12 (Visit 6, EOT)	Week 12	85	71-91
Week 14/16 (Visit 7, EOS)	Week 14/16	99	>91

Study days are calculated considering Day 1 as the day of first administration of intervention (or the day of randomization for participant not exposed).

Table 9 - Time-window definition for efficacy endpoints analyses

Scheduled visit	Analysis visit	Targeted study day	Time-window (days)	
			Disease Assessment (including PASI, sPGA, BSA and PPASI)	Disease Assessment (including NAPSI)
Week 4 (Visit 5)	Week 4	29	2-42	
Week 8 (Visit 6)	Week 8	57	43-70	
Week 12 (Visit 7, EOT)	Week 12	85	>70	>1

Study days are calculated considering Day 1 as the day of first administration of intervention (or the day of randomization for participant not exposed).

Table 10 - Time-window definition for patient reported outcomes measures analyses

Scheduled visit	Analysis visit	Targeted study day	Time-window (days)	
			DLQI, PGIS, PGIC, PQATv2	PSSD, Joint-Pain NRS, Joint Stiffness NRS, FACIT-Fatigue
Week 2 (Visit 4)	Week 2	15		2-21
Week 4 (Visit 5)	Week 4	29		22-42
Week 8 (Visit 6)	Week 8	57		43-70
Week 12 (Visit 7, EOT)	Week 12	85	>1	>70

Study days are calculated considering Day 1 as the day of first administration of intervention (or the day of randomization for participant not exposed).

Table 11 - Time-window definition for PK endpoints analyses

Scheduled visit	Analysis visit	Targeted study day	Time-window (days)	
			PK Assessments	
Week 0 (Visit 2)	Week 0	1	2.5-3.5 hour after Day 1 dose	
Week 2 Pre-dose (Visit 3)	Week 2	15	1 hour before Day 7-21 dose	
Week 2 Post-dose (Visit 3)	Week 2	15	2.5-3.5 hour after Day 7-21 dose	
Week 4 Pre-dose (Visit 4)	Week 4	29	1 hour before Day 22-42 dose	
Week 4 Post-dose (Visit 4)	Week 4	29	2.5-3.5 hour after Day 22-42 dose	
Week 8 Pre-dose (Visit 5)	Week 8	57	1 hour before Day 43-70 dose	
Week 8 Post-dose (Visit 5)	Week 8	57	2.5-3.5 hour after Day 43-70 dose	
Week 12 Pre-dose (Visit 6)	Week 12	85	1 hour before Day >70 dose	
Week 12 Post-dose (Visit 6)	Week 12	85	2.5-3.5 hour after Day >70 dose	

Study days are calculated considering Day 1 as the day of first administration of intervention (or the day of randomization for participant not exposed).

Unscheduled visits

Unscheduled visit measurements of laboratory data, vital signs, ECG and ADA will be used for computation of baseline, the last on-treatment value, analysis according to PCSAs, and the shift summaries for safety. They will also be included in the by-visit summaries if they are re-allocated to scheduled visits.

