- k When several assessments take place at the same visit, the following order is recommended: Patient Reported Outcome Measures (Questionnaires), Triplicate ECG (after 10min of rest), Blood sampling, Urine test (when applicable), IMP administration, Vital signs, Physical examination, Clinical assessments, IMP compliance check, verification of the Medication Intake Questionnaire (paper), Prior and concomitant medications, AE reporting, IMP dispensed for home administration. And during Post-IMP PK blood sampling visits, conclude with Triplicate ECG (after 10min of rest and within 15min prior to PK blood sampling), followed by PK blood sampling.
- l Dispensed with Medication Intake Questionnaire (paper).
- m Compliance will be assessed by the investigator by direct questioning, verifying the Medication Intake Questionnaire (paper), and counting returned tablets in each pack during the site visits and documented in the source documents and relevant form. Deviations from the prescribed dosage regimen must be recorded.
- n Questionnaire provided to the trial participant on D1 and at each visit, then returned by the participant at each visit and checked by the investigator to verify the IMP intake and potential adverse events.
- o Clinical assessments should be completed by the same physician for a given participant, if possible, to secure longitudinal comparison and avoid any bias.
- p BSA will be extracted from PASI assessment ([Section 8.2.3](#)).

s Refer to [Section 5.3.2](#) for further details.

*t* Refer to Section 8.3.6 – Pregnancy testing for instruction on timepoints

v Hematology: RBC, RBC indices, hemoglobin, hematocrit, thrombocyte count (platelets), leukocyte count (white blood cell count) with differential in absolute counts (including neutrophils, eosinophils, basophils, lymphocytes (including CD4 count), monocytes).

Clinical chemistry: Sodium, potassium, chloride, bicarbonate, blood urea nitrogen (BUN), creatinine, creatinine clearance, CPK, calcium, phosphate, total protein, albumin, alanine aminotransferase (ALT), aspartate aminotransferase (AST), alkaline phosphatase (ALP), total bilirubin, conjugated bilirubin, unconjugated bilirubin, glucose (non-fasting).

w Fasting total cholesterol, fasting triglycerides, HDL, and LDL. Participant must be fasting for 8 hours prior to laboratory testing (may consume water). A light meal will be provided by the site after the laboratory tests, lipids panel and pre-dose-PK.

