Overall, SAR441566 showed consistent PK and PD characteristics which support advancement into further clinical studies in participants. Both QD and BID dosing without regard to food are deemed feasible considering SAR441566  $t_{1/2z}$  of approximately 20 to 30 hours, negligible food effect at 200 mg single dose. High target occupancy was observed across the investigated dose levels in the MAD study (100 mg QD, 100/200/300 mg BID). The published estimates of TNF $\alpha$  occupancy indicate >98% for marketed TNF $\alpha$  inhibiting biologics (13) at average steady state concentration of efficacious dose. The mean TNF $\alpha$  occupancy measured on Day 14 was ~95% for 100 mg QD and at pre-dose (trough level) and ~100% for all other time points assessed across the investigated dose range, ie, at 3 hours post-dose (~Cmax) for 100 mg QD, at pre-dose and 3 hours post-dose for 100 mg, 200 mg and 300 mg BID, respectively, which is in line with the exposure-occupancy relationship established by *in vitro* studies (see also IB Section 5.1.2.4). These results suggest that 100 mg to 400 mg total daily doses can be considered potential therapeutically relevant doses. 50 mg QD is considered a sub-therapeutic dose based on the target occupancy results of doses >100 mg.

In the POM study (PDY16918) in participants with mild to moderate psoriasis, serum IL-17A, IL-17F and IL-22 levels markedly declined following 4-week treatment of 200 mg BID SAR441566, in contrast to placebo. Notably, the biomarker decreases were in line with the observed clinical improvement in TLS score of 17.7% with 90% CI [4.98 to 30.49] at Week 4 compared to placebo. The adjusted mean % improvement of 19.4% with 90% CI [6.28 to 32.48] in PASI at Week 4 was consistent with the clinically relevant improvement in the TLS score. The results obtained in the proof-of-mechanism study support the initiation of Phase 2 dose ranging studies as part of the further clinical development of SAR441566.

In summary, the dose levels selected for the current study are expected to be safe and, based on the target occupancy data from the MAD study, as well as the efficacy and biomarker outcomes from the proof-of-mechanism study, to span a range of potential therapeutically relevant as well as subtherapeutic doses which will allow to explore the dose-response relationship and the determination of the optimal therapeutic dose for future large-scale studies.

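### The by-visit QTcF summaries are pre-dose only when ECGs follow the recommended order, and no planned table shows QTcF by arm at a labelled near-peak timepoint

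*SAP*

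**What the plan says.** Protocol 1.3, footnote k, recommends an order of assessments within a visit: "Triplicate ECG (after 10min of rest), Blood sampling, Urine test (when applicable), IMP administration, Vital signs". The first triplicate ECG therefore precedes the dose. For visits with post-dose PK sampling the footnote adds that they should "conclude with Triplicate ECG (after 10min of rest and within 15min prior to PK blood sampling), followed by PK blood sampling".

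SAP 5.4, Table 11, times the post-dose PK samples: "2.5-3.5 hour after Day 1 dose" at Week 0 and, for example, "2.5-3.5 hour after Day 7-21 dose" at Week 2, with the same hours at Weeks 4, 8 and 12. Protocol 4.3 treats that time as close to peak: "at 3 hours post-dose (~Cmax) for 100 mg QD".

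SAP 5.4, Table 8, has one column of day windows for "Vital signs, laboratory tests, 12-lead ECG and Targeted Physical examination", starting at Day 2, with no separation of pre-dose from post-dose. Two rules reduce multiple values to one. The first is "if multiple assessments are associated to the same time point, the closest from the targeted study day will be used". The second is "If multiple valid values exist within a same day, then the first value of the day will be selected".

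SAP 3.6.3.1 averages the tracings of a triplicate. It plans descriptive statistics by visit, for the last on-treatment value and for the worst on-treatment value. PCSA analyses use every measurement in the treatment-emergent period. The SAP version history records that a concentration-ECG section was removed in version 2.

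**The concern.** A second triplicate placed just before a near-peak PK sample is there to observe the heart when exposure is highest. A same-day rule that always favours the earlier ECG sends the trough reading into the by-visit table and leaves the near-peak reading out. In a dose-ranging trial, that table is where a reader would look for a dose-related shift in mean QTcF. QT is a recognised topic here: exclusions E 07 and E 26 concern it, and the protocol carries a list of QT-prolonging drugs.

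Trough-only rows may also treat the regimens unequally, because a once-daily trough lies further below its peak than a twice-daily trough. With the concentration-ECG section gone, no other SAP analysis is tied to the near-peak time.

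**Working it through.** The plan states no figure to reproduce. The check applies the SAP 5.4 rules to the footnote k sequence.

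1. **Two scheduled values on one day.** Both triplicates are scheduled, so the restriction of by-visit ECG analyses to scheduled measurements removes neither.
2. **Distance from target day.** Both fall on the same study day, so they are equally far from the target and the closest-day rule cannot separate them.
3. **Same-day rule.** It selects the first, which is the pre-dose triplicate. Averaging in SAP 3.6.3.1 works within a triplicate and does not choose between two of them.
4. **Day 1.** SAP 3.1 takes baseline as the last value before the first dose, so the pre-dose ECG is baseline. The post-dose ECG cannot be baseline, and Table 8 starts at Day 2, so it has no row.

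| Visit | Table 8 window (days) | Value in the by-visit row | Post-dose triplicate, if taken |
|---|---|---|---|
| Day 1 | none | pre-dose, as baseline | no row |
| Week 2 | 2-21 | pre-dose | not selected |
| Week 4 | 22-42 | pre-dose | not selected |
| Week 8 | 43-70 | pre-dose | not selected |
| Week 12 | 71-91 | pre-dose | not selected |

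As scheduled, 0 of at most 1 + 4 = 5 post-dose triplicates enter a by-visit row. Five is an upper bound, taken from Table 11.

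**Where post-dose ECGs still count.** The worst-value summary and the PCSA counts include them. For the last value, Protocol 1.3 has the Week 12 dose taken on site, and the on-treatment period ends one day after the last dose. If Week 12 has a post-dose ECG, it would be a completer's last on-treatment value. The Week 12 row would then be trough and the last-value row near-peak, with neither labelled. SAP 5.4 ties its windows to by-visit analyses and does not say whether the same-day rule also governs the last value.

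**How far trough lies from peak.** Protocol 4.3 gives a half-life of about 20 to 30 hours and a peak near 3 hours. Assume mono-exponential decline after 3 hours. The ratio of pre-dose to 3-hour concentration is then 2^(-Δ/half-life), with Δ = 24 - 3 = 21 h for QD and 12 - 3 = 9 h for BID:

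- QD: 2^(-21/20) = 0.483 to 2^(-21/30) = 0.616
- BID: 2^(-9/20) = 0.732 to 2^(-9/30) = 0.812

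Under this assumption the by-visit rows reflect about 48-62% of near-peak concentration on QD and 73-81% on BID. These are concentration ratios, not QTcF effects.

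**The case against.** The strongest reply is that little is lost. SAP 3.6.3.1 describes change from baseline for the last and worst values with means and standard deviations, by arm and alongside placebo, so a mean shift can show there. The last-value row may itself be near-peak for completers. The secondary endpoint counts participants with medically significant changes, and the PCSA analyses that serve it use all measurements. Protocol 2.3.1 reports no QTc event of special interest in completed Phase 1 studies up to 600 mg single dose or 300 mg BID. All of this stands, and it limits the severity.

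A second reply is that the visit schedule is uncertain. Footnote k only recommends an order. The ECG timing text in Protocol 8.3.3 is redacted, the PK footnotes are not visible, and the Schedule of Activities uses three different footnote marks across five PK visits. This also stands: the number of affected visits is at most five, and a missing pre-dose ECG at Weeks 2 to 12 would let the post-dose one in.

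A third reply is that pre-dose and post-dose are naturally separate timepoints, and Protocol 8.3.3 has each ECG file labelled with its theoretical day and time. The labels do exist, but Table 8 does not use them, whereas Table 11 makes exactly this split for PK. Protocol 8.5 allows exposure-response work in a separate report, but only as a possibility and without naming ECG.

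**Conclusion.** The point holds for the by-visit QTcF rows. With ECGs in the recommended order, those rows are pre-dose only, and up to five near-peak triplicates per participant do not enter them. No planned table gives mean QTcF change by arm at a labelled near-peak time. The last-value and worst-value rows are partial substitutes: the first has an undefined position relative to dosing, and the second is an extreme taken across visits and times.

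A reader might infer that the near-peak ECGs drop out of the safety analysis, or that the secondary ECG endpoint is compromised. The documents do not support either: PCSA and worst-value analyses keep these ECGs, and the endpoint is a participant count. Nor can the understatement be put in milliseconds, because the documents give no QTcF effect and no concentration-QTcF relation.

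Severity is low to moderate. The conclusion rests on footnote k being followed and on Table 11 reflecting the visits with a post-dose ECG.

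**What to change.** In SAP 5.4:

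- Split the ECG rows of Table 8 into pre-dose and post-dose timepoints for every visit with a post-dose ECG, as Table 11 does for PK.
- Add a Day 1 post-dose row.
- Apply the first-of-day rule within each timepoint only.
- Report QTcF change from baseline by arm at both timepoints, and state which one the last-value row draws on.

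The post-dose ECG window should not simply copy Table 11's hours. The ECG may precede the PK sample by up to 15 minutes, so a sample at 2.5 h can have its ECG at 2.5 - 0.25 = 2.25 h. A window of 2.25 to 3.5 h would match.

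The cost is SAP wording, some programming and a few extra table rows. The ECGs are already scheduled, and no efficacy analysis changes.
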